### 5.12.1 Primary Endpoint

The primary efficacy endpoint is the confirmed Objective Response Rate (ORR) defined according to RECIST v1.1. ORR is defined as the proportion of patients with a confirmed objective response of CR or PR.

Hypothesis testing will be performed to compare the ORR between both treatment groups. The null hypothesis is that the ORR of the combination treatment arm is superior to that of the control treatment arm:

*Null hypothesis:  $H_0: ORR_{comb} \leq ORR_{con}$*

*Alternative hypothesis:  $H_1: ORR_{comb} > ORR_{con}$*

### 5.12.2 Primary Efficacy Analysis

The primary efficacy analysis for ORR will be conducted once all patients are treated and followed for a minimum of 3 months (2 radiologic scans).

The number and percentage of patients with each BOR category will be summarized.

The ORR will be defined as the proportion of patients with a confirmed objective response as assessed by the Investigator in the FAS. “Patients who receive at least one dose of either study

QMD Ref: Worldwide-TMP-ST-054-1.0_Effective: 12Aug2022	Governing QMD: Worldwide-SOP-ST-026
Confidentiality Statement	

This document is the property of Worldwide Clinical Trials Inc. and may not be duplicated, copied, altered or removed from company without prior approval from Worldwide Quality Assurance or in compliance with Worldwide Standard Operating Procedures.

Worldwide Clinical Trials Controlled Quality Management Document			
 WORLDWIDE CLINICAL TRIALS	Sponsor:	Flamingo Therapeutics	
	Protocol Number:	FLM-6774-201	
STATISTICAL ANALYSIS PLAN			

treatment but have no valid post-baseline tumor assessment or not available confirmed BOR will be considered non-responders.”

The ORR estimate along with the corresponding 2-sided 90% and 95% confidence interval using Clopper-Pearson exact binomial test will be presented for each treatment arm.

Comparison of the ORR between treatment arms will be analyzed using Fisher’s Exact test and by reporting the risk difference and corresponding 90% and 95% confidence intervals. Both a 1-tailed and 2-tailed p-value for Fisher’s Exact test will be provided. The risk difference for ORR is calculated as the difference in ORR between both treatment arms. Confidence intervals for the risk difference will be calculated using the Wald Method.

The following SAS code will be used, where adrs\_freq is a frequency table of planned treatment by responder status. (Sorted so that first row is responders for the combination arm).

ORR Estimate and Corresponding Exact Binomial Confidence Intervals:

```
ods output binomial=<outdata>;
proc freq data=adrs_freq;
  tables avalc / binomial(level="RESPONDER") alpha=0.05;
  by trt01pn;
  weight count;
run;
Lower Limit is nvalue1 where name1="XL_BIN".
Upper Limit is nvalue1 where name1="XU_BIN".
Use alpha=0.10 for 90% CI.
```

Risk Difference and Corresponding Confidence Intervals:

```
ods output riskdiffcol2=<outdata>;
proc freq data=adrs_freq order=data;
  tables trt01pn*avalc / riskdiff alpha=0.05;
  weight count;
run;
Use risk, lowercl, and uppercl where row="Difference".
Use alpha=0.10 for 90% CI.
```

Fisher’s Exact Test:

```
ods output fishersexact=<outdata>;
proc freq data=adrs_freq order=data;
  tables trt01pn*avalc / fisher;
  weight count;
run;
For 1-tailed test, nvalue1 where name1="XPR_FISH".
For 2-tailed test, nvalue1 where name1="XP2_FISH".
```

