Patients in both treatment arms will have radiologic tumor assessments every 6 weeks (± 1 week), regardless of treatment delays, until objective disease progression, initiation of new anticancer treatment, death, withdrawal of consent, or end of study, whichever occurs first.

All patients who discontinue study treatment for any reason will have a safety follow-up visit 30 days (+7 days) after the last dose of study treatment and a follow-up for AEs 90 days (+7 days) after the last dose of pembrolizumab. Patients will be followed for survival at 12-week (± 7 days) intervals until death or withdrawal of consent, whichever occurs first. Survival follow-up will continue until at least 15 months after the last patient is randomized in the study.

The study design is depicted in [Figure 1](#).

Figure 1: Study Scheme

Note: Maximum duration of pembrolizumab treatment is 24 months; there is no limit to the duration of danvatirsen treatment.

Abbreviations: PD = progressive disease; Q3W = every 3 weeks; QW = weekly; SFU = safety follow-up & survival follow-up

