7.7 Imaging Assessments

For all patients, tumor response assessment will be obtained by radiographic imaging with contrast-enhanced CT (preferred) or MRI evaluation. Optimal anatomic coverage for most solid tumors include the chest, abdomen, and pelvis. Coverage should encompass all areas of known predilection for metastases in the disease under evaluation and should additionally investigate areas that may be involved based on signs and symptoms of individual patients. In general, lesions present at baseline should be followed using the same imaging methodology and imaging equipment at subsequent assessments.

Tumor response assessments will be based on evaluation of response of target, non-target, and new lesions according to RECIST v1.1, as detailed in [Appendix 5](#) (all measurements should be recorded in metric notation). Following initial objective response (PR or CR per RECIST v1.1), confirmatory imaging studies should be obtained 4 to 6 weeks later ([Eisenhauer et al 2009](#)).

Before stopping treatment, confirmation of PD should be considered by imaging no less than 4 weeks after initial progression.

The timing of on-study imaging should follow calendar days and **should not** be adjusted for delays in treatment administration or for visits. The same imaging technique should be used in a patient throughout the study for consistency.

For patients who discontinue study treatment for reasons other than PD, radiographic scans should continue according to the respective schedule of assessment until PD, initiation of new anticancer therapy, withdrawal of consent, or at least 15 months after the last patient is

randomized in the study, whichever comes first. Additional imaging may be performed if clinically indicated per the Investigator's discretion.

Brain MRI with or without contrast is the preferred brain imaging modality; however, CT is acceptable if MRI is clinically contraindicated. Patients with treated or untreated parenchymal brain metastases, leptomeningeal disease, or current active malignant epidural disease are excluded from participation in the study (see [Section 4.2](#)). Patients with previously treated epidural disease are allowed as long as disease is inactive. Patients are not required to have brain imaging at screening unless there are suggestive clinical symptoms/suspicion.

During the study, brain CT/MRI scans should be conducted if clinically indicated by development of new specific symptoms.

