9.7 Analysis of Efficacy

The primary efficacy analysis for ORR, as well as the interim analysis for PFS and OS, will be conducted once all patients are treated and followed for a minimum of 3 months (2 radiologic scans). The final analysis for PFS and OS will be conducted after all patients have been followed for a minimum of 15 months, unless the study is deemed futile at the interim or primary analysis stage.

The overall response will be assessed by the Investigator based on the RECIST v1.1 criteria at each timepoint specified the SoA ([Section 8.1](#)). The best overall response (BOR) will be assessed from response assessments occurring after the first dose of either study treatment up to the first documented assessment of PD that is prior to the initiation of a new anticancer therapy. Objective response (i.e., BOR of PR or CR) will require confirmation of the response (CR or PR) at least 4 weeks after the initial CR or PR.

The ORR will be defined as the proportion of patients with a confirmed objective response as assessed by the Investigator in the FAS. Patients who receive at least one dose of either study treatment but have no valid postbaseline radiographic assessment will be considered non-responders. The ORR will be reported along with the corresponding 2-sided 90% and 95% Clopper-Pearson exact CI. The criteria for promising ORR at the primary analysis are detailed in [Table 9](#) and, in addition, a comparison between the 2 treatment groups will be performed based on Fisher's exact test.

DOR is defined as the date of the patient's first confirmed BOR of CR or PR to the earliest date of documented progression or death if no prior evidence of disease progression, for all patients in the FAS with a confirmed objective response. A patient that starts a new anticancer therapy prior to disease progression will be censored at the date of last valid disease assessment prior to the start of the new anticancer therapy. All other patients without progression or death will be censored at the date of the last valid disease assessment. DOR will be summarized using Kaplan-Meier methods.

The DCR, which includes a BOR of CR, PR, or SD, will be analyzed similar to ORR.

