## 5.12 Efficacy Analyses

All efficacy analyses will be presented by planned treatment for the FAS.

All statistical tests will be performed using a two-tailed 5% overall significance level, unless otherwise stated. All comparisons between treatments will be reported with 90% and 95% confidence intervals for the difference.

The following efficacy parameters will be derived as per RECIST v1.1 for the FAS.

- Overall Response Rate
- Disease Control Rate
- Complete Response Rate
- Duration of Response
- Progression-Free Survival
- Overall Survival

A summary of RECIST v1.1 tumor assessments, methods, and criteria are presented in Appendix 5 of the protocol. All efficacy parameters are derived from overall response as per RECIST v1.1. Overall response at each tumor assessment is determined using measurements of both target and non-target lesions. The overall response categories are as follows.

All target lesion, non-target lesion, and new lesion data will be listed separately.

Overall Response Categories by RECIST v.1.1	
CR	Complete Response
PR	Partial Response
SD	Stable Disease
PD	Progressive Disease
NE	Not Evaluable

A response of CR or PR must be confirmed by a repeat assessment at least 4 weeks after the initial CR or PR. A tumor assessment at least 35 days after the first dose is required for an overall response of SD, otherwise the BOR is considered not evaluable (NE).

Overall response rate (ORR), complete response rate (CR), and disease control rate (DCR) are each calculated using the subject's best overall response (BOR) on study. This is determined based on the following hierarchy for overall response category:

CR > PR > SD > PD > NE

Tumor assessments after the first PD will not be considered for BOR.

QMD Ref: Worldwide-TMP-ST-054-1.0_Effective: 12Aug2022	Governing QMD: Worldwide-SOP-ST-026
Confidentiality Statement	

This document is the property of Worldwide Clinical Trials Inc. and may not be duplicated, copied, altered or removed from company without prior approval from Worldwide Quality Assurance or in compliance with Worldwide Standard Operating Procedures.

Worldwide Clinical Trials Controlled Quality Management Document			
 WORLDWIDE CLINICAL TRIALS	Sponsor:	Flamingo Therapeutics	
	Protocol Number:	FLM-6774-201	
STATISTICAL ANALYSIS PLAN			

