When a patient has at least one overall response of CR or PR, BOR will be assigned using the following rules. This algorithm is not applied for analyses based on unconfirmed response.

(See [Section 5.12.5](#))

Overall Response	Overall Response of Subsequent Assessment	Best Overall Response (Confirmed)
CR	CR $\geq$ 4 weeks later	CR
CR	PR, SD, or PD	SD if duration criteria* PD otherwise
CR	No Evaluable Assessment	SD if duration criteria* NE otherwise
PR	CR $\geq$ 4 weeks later	PR
PR	PR $\geq$ 4 weeks later	PR
PR	SD	SD
PR	PD	SD if duration criteria* PD otherwise
PR	No Evaluable Assessment	SD if duration criteria* NE otherwise

\* Assessment occurred a minimum of 35 days since Baseline

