## 9 CHANGES TO PLANNED PROTOCOL ANALYSIS

The final analysis analysis will occur prior to the conditions outlined in Section 8, due to early termination of the study.

QMD Ref: Worldwide-TMP-ST-054-1.0_Effective: 12Aug2022	Governing QMD: Worldwide-SOP-ST-026
Confidentiality Statement	
This document is the property of Worldwide Clinical Trials Inc. and may not be duplicated, copied, altered or removed from company without prior approval from Worldwide Quality Assurance or in compliance with Worldwide Standard Operating Procedures.	

Worldwide Clinical Trials Controlled Quality Management Document		
 WORLDWIDE CLINICAL TRIALS	Sponsor:	Flamingo Therapeutics
	Protocol Number:	FLM-6774-201
STATISTICAL ANALYSIS PLAN		

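### The ORR analysis may start at 3 months (2 scans), too early to confirm a response first seen at scan 2; the planned effect is small, but SAP section 9 sets no replacement cut-off

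*SAP*

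**What the plan says.** **Trigger.** SAP 5.12.2 runs the primary ORR analysis when all patients have been treated and "followed for a minimum of 3 months (2 radiologic scans"). SAP sections 3 and 8 and protocol 9.2 and 9.7 give the same minimum.

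**Scans.** Protocol 3.1 schedules "radiologic tumor assessments every 6 weeks (± 1 week") in both arms, regardless of treatment delays.

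**Confirmation.** Protocol 9.7 says that objective response "will require confirmation of the response (CR or PR) at least 4 weeks after the initial CR or PR". SAP 5.12 agrees: "A response of CR or PR must be confirmed by a repeat assessment at least 4 weeks after the initial CR or PR". Protocol 7.7 adds that "confirmatory imaging studies should be obtained 4 to 6 weeks later".

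**Scoring.** In the SAP 5.12 table of confirmed best overall response, a CR or PR with no later evaluable assessment becomes "SD if duration criteria* NE otherwise". The footnote defines the duration criterion: "Assessment occurred a minimum of 35 days since Baseline". SAP 5.12.2 keeps patients without an available confirmed best response in the denominator as non-responders.

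**Early termination.** SAP section 9 states that the final analysis "will occur prior to the conditions outlined in Section 8, due to early termination of the study". For the final ORR analysis, section 8 requires both 81 patients and the 3-month minimum. Section 9 does not say which of the two is unmet and gives no other cut-off or minimum follow-up.

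**Existing sensitivity analysis.** SAP 5.12.5 repeats ORR and DOR without requiring confirmation (Table 14.2.1.8 for ORR).

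**The concern.** The trigger guarantees two scans, but confirming a response first seen on the second scan needs a third. The most recently enrolled patients can therefore be counted as failures because the clock stopped, not because the tumor failed to respond. Neither document has a rule for responses still awaiting confirmation.

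The error runs one way. It lowers the confirmed ORR in both arms, and if the same proportion is lost in each it also shrinks the difference and costs power. The size depends on how many patients are close to the minimum at the cut-off. That is why the silence in SAP section 9 matters: the analysis that will now be done has no stated minimum follow-up.

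**Working it through.** **1. The plan's own figure.** I enumerated the two-stage BOP2 rule exactly.
- Inputs (protocol 9.2): 13 vs 26 patients at the interim and 27 vs 54 at the end; Beta(0.5, 0.5) priors; interim threshold 0.96 × (39/81)^0.94 = 0.483; final threshold 0.96.
- The boundaries match every row of Table 9.
- At 15% vs 43%, power is 82.6% (stated 83%; Table 10 gives 82.7%) and early stopping is 1.9% (Table 10: 1.9%).
- At 15% vs 15%, type I error is 4.5% (Table 10: 4.6%).

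**2. Calendar check, no assumptions.** Three months = 3 × 365.25/12 = 91.3 days = 13.04 weeks.

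| Scan 2 at | Earliest confirmation (+4 weeks) | Short of it at 13.04 weeks by | Latest confirmation (+6 weeks) |
|---|---|---|---|
| Week 11 | Week 15 | 2.0 weeks | Week 17 |
| Week 12 | Week 16 | 3.0 weeks | Week 18 |
| Week 13 | Week 17 | 4.0 weeks | Week 19 |

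No permitted timing lets a patient with only the minimum follow-up confirm a scan-2 response. A response first seen at scan 1 can be confirmed at scan 2.

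**3. How it is scored.** Scan 2 falls on days 77 to 91, which always exceeds 35 days. The table therefore gives stable disease, and SAP 5.12.2 counts a non-response.

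**4. Size at the planned trigger.** The documents give neither the accrual pattern nor the timing of responses. Assume uniform accrual over 52 to 104 weeks, 20 to 40% of responses first seen at scan 2, and 16 to 18 weeks needed for confirmation.
- Share of patients short of time = (weeks needed − 13) / accrual weeks. Low: 3/104 = 2.9%. High: 5/52 = 9.6%.
- Share of responses lost = that share × share first seen at scan 2. Low: 2.9% × 0.20 = 0.6%. High: 9.6% × 0.40 = 3.8%.
- Points lost from a 43% ORR: 43 × 0.006 = about 0.2; 43 × 0.0385 = about 1.7.
- One of 54 combination patients is 1.85 points, so even the high figure is about 0.9 of a responder.

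**5. Effect on the decision rule.** These figures assume that the same proportion of responses is lost in both arms and that 81 patients are analyzed.

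| Responses lost | Power | Type I error |
|---|---|---|
| 0% | 82.6% | 4.5% |
| 1% | 82.0% | 4.6% |
| 4% | 80.4% | 4.6% |
| 10% | 77.2% | 4.7% |
| 20% | 71.4% | 4.9% |

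The range in step 4 lies within the first three rows. The last two rows show how power would respond to a larger loss; they are not estimates for this trial.

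**The case against.** **Three months is a minimum.** Most patients will have been followed longer when the last one reaches it, and their scan-2 responses can be confirmed. This stands, and it is why the planned effect is below one combination-arm responder. Nor does the SAP state a data cut for tumor assessments at the primary analysis (section 8 states one only for the interim), so later scans might be included. Nothing requires that, however.

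**The sensitivity analysis already covers it.** SAP 5.12.5 counts a pending scan-2 response as a response, so the gap between the two ORRs shows how much confirmation matters. This stands in part. The analysis drops confirmation for everyone, so it mixes responses that lacked time with responses that had time and failed. It also leaves the primary estimate unchanged.

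**Any cut-off leaves some responses pending.** With an 18-week minimum, a response first seen at scan 3 (week 18) needs weeks 22 to 24. This also stands. The longer minimum reduces the loss but does not end it.

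**A stronger reading of SAP section 9.** A reader might infer that section 9 abandons the 3-month minimum and that a large share of patients will lack time. With a cut-off at the end of a 52- to 104-week uniform accrual, 18/104 to 18/52, or 17 to 35%, would lack 18 weeks. The documents do not support this as a finding. Section 8 combines 81 patients with 3 months, and stopping short of 81 would satisfy section 9 even if every patient had 3 months or more. Both the cut-off and the accrual period in that calculation are assumed.

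**Conclusion.** The mechanism follows from the documents alone: for a patient with only the minimum follow-up, a response first seen at scan 2 cannot be confirmed and is counted as a non-response.

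At the planned trigger the effect is probably small. About 3 to 10% of patients would be short of time, at a cost of up to about 1.7 points of a 43% ORR and roughly 2 points of power, with little effect on type I error. These figures rest on the assumed accrual, the assumed timing of responses and equal proportional loss in the two arms. They do not support reading this as inflation of the false-positive rate or as a reason to discard the primary analysis.

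For the early-termination analysis the loss could be larger if follow-up is shorter. With less than about 12 weeks, even scan-1 responses might not be confirmable. The documents give neither the cut-off nor the number enrolled, so that size cannot be computed. The clear defect in SAP section 9 is that it does not say which condition fails and puts no minimum follow-up in its place.

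**What to change.** 1. Where still possible, set the ORR cut-off at a minimum of 18 weeks after the last patient's first dose, or 19 weeks to cover the scan window (week 13 + 6).
2. In SAP section 9, state the actual cut-off, the minimum follow-up at that date, and whether the 81-patient condition, the 3-month condition or both are unmet.
3. For the early-termination analysis, keep the all-FAS result as it is. Beside it, add confirmed ORR in both arms restricted to patients first dosed at least 18 to 19 weeks before the cut-off. The restriction uses only the first-dose date, so it does not select on outcome, and it separates lack of time from failed confirmation.
4. Make the change by SAP amendment before database lock; after lock, SAP section 5 sends it to an addendum.

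The cost is about 5 to 6 weeks' delay (18 − 13 or 19 − 13), or one extra table from data already collected, with a smaller N. Responses first seen at scan 3 or later may still be unconfirmed.

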#### 5.12.4.1 Disease Control Rate and Complete Response Rate

Disease control rate (DCR) is defined as the proportion of patients with a best overall response of CR, PR, or SD. Confirmation by repeat assessments is required for a BOR of CR or PR.

Complete response rate (CRR) is defined as the proportion of patients with a best overall response of CR. Confirmation by repeat assessments is required.

The statistical analysis of DCR and CRR will be the same as performed for ORR described in [Section 5.12.2](#).

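### The SAP code for the primary ORR difference reads the non-responder column, so a benefit is reported as a negative difference with a sign-reversed confidence interval

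*SAP*

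**What the plan says.** SAP section 5.12.2 defines the risk difference as the difference in ORR between the arms, with Wald intervals at 90% and 95%, and prints the SAS code to be used.

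- **Input data.** A frequency table of planned treatment by responder status: "Sorted so that first row is responders for the combination arm".
- **Procedure and table.** "proc freq data=adrs_freq order=data", then "tables trt01pn*avalc / riskdiff alpha=0.05".
- **Output table kept.** "ods output riskdiffcol2=<outdata>".
- **Values taken.** "Use risk, lowercl, and uppercl where" the row is labelled Difference. No negation or relabelling follows.
- **Fisher's test.** The same data, the same `order=data` and the same table. "For 1-tailed test, nvalue1 where" the name is `XPR_FISH`, the right-sided p-value.

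SAP section 5.12.1 puts benefit in the direction of a higher ORR on the combination. Section 5.12.3 analyses all secondary rates like the primary endpoint, and section 5.12.4.1 repeats this for disease control rate (DCR) and complete response rate (CRR): "The statistical analysis of DCR and CRR will be the same as performed for ORR described in" section 5.12.2.

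**The concern.** With the stated sort and `order=data`, row 1 is the combination arm and column 1 is RESPONDER. The RiskDiffCol2 table holds the proportions in column 2, which are the non-response rates. The Difference row of that table is the non-response rate on the combination minus that on pembrolizumab, which is the ORR difference with its sign reversed.

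The primary efficacy table would then show a one-tailed p-value in favour of the combination beside a difference and two intervals that, read in the usual direction, indicate harm. The same would happen for DCR and CRR. It would probably also happen in the subgroup tables of section 5.12.6 and the ORR/DCR forest plot of section 5.12.8, where a reversed sign is hardest to notice.

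**Working it through.** **Inputs**

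- Design ORRs: 0.43 combination, 0.15 control (SAP section 3).
- Sample size: 81 at 2:1, so 54 and 27 (SAP section 3; protocol Table 9).
- Illustrative counts, assumed because the documents give none: 23/54 and 4/27, close to the design rates.
- SAS conventions, assumed because the documents do not explain them: RiskDiffCol1 and RiskDiffCol2 refer to columns 1 and 2; Difference is row 1 minus row 2; `XPR_FISH` is the right tail for cell (1,1).

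**The plan's own figures.** The documents state no ORR difference or interval for this code to reproduce. The design figures do reproduce: exact enumeration of the two-stage rule at 0.43 versus 0.15 gives 82.6% power (protocol Table 10: 82.7%) and, at 0.15 in both arms, 4.5% type I error (Table 10: 4.6%). So 54 versus 27 is a fair basis for illustration.

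**Step 1: what column 2 holds**

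(1 - ORRcomb) - (1 - ORRcon) = ORRcon - ORRcomb

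At the design rates: 0.57 - 0.85 = -0.28, where the ORR difference is 0.43 - 0.15 = +0.28.

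**Step 2: illustrative counts**

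- Correct difference: 23/54 - 4/27 = 0.4259 - 0.1481 = +0.2778
- SE = sqrt(0.4259 × 0.5741/54 + 0.1481 × 0.8519/27) = 0.0959
- 95% CI: 0.2778 ± 1.960 × 0.0959 = 0.090 to 0.466
- 90% CI: 0.2778 ± 1.645 × 0.0959 = 0.120 to 0.436
- As coded: 31/54 - 23/27 = 0.5741 - 0.8519 = -0.2778, same SE, 95% CI -0.466 to -0.090, 90% CI -0.436 to -0.120

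**Step 3: can another table order rescue the code?** The column-2 difference and the one-tailed Fisher p-value for the same counts, in all four layouts:

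| Row 1 | Column 1 | Column-2 difference | `XPR_FISH` p |
|---|---|---|---|
| Combination | Responder (the SAP's sort) | -0.278 | 0.0103 |
| Pembrolizumab | Non-responder | -0.278 | 0.0103 |
| Combination | Non-responder | +0.278 | 0.998 |
| Pembrolizumab | Responder | +0.278 | 0.998 |

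The right-tail p-value tests whether the column-1 proportion is higher in row 1, and the column-2 difference is always the negative of the column-1 difference. The two blocks therefore conflict in every layout: either the difference has the wrong sign, or the one-tailed p-value tests the wrong direction.

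**The case against.** - **Direction is not stated.** The SAP does not say which arm is subtracted from which, so pembrolizumab minus combination is arithmetically a difference in ORR with a valid Wald interval. The table shells, which might label it, are not among the documents. This stands as a gap in the text, but it does not save the code: the alternative hypothesis and the sort both put the combination first, and no such label appears in the SAP.
- **No test or decision changes.** This stands. Under the SAP's sort both Fisher p-values are right. The Clopper-Pearson intervals name the RESPONDER level explicitly and are right. The posterior-probability rule does not use this code. The size of the difference, the interval width and whether it excludes zero are unchanged.
- **It would be noticed.** The same analysis reports both ORRs, so 42.6% and 14.8% would appear with -27.8. The ORR table is also independently programmed by a statistician (SAP section 11), and at least one printed block, the Cox model in section 5.12.4.3, needs editing before it will run because a semicolon is missing. These points make an undetected error less likely. But the risk-difference block as printed would run without an error, and two programmers following the same specification would agree on the wrong sign.
- **Reach is partly inferred.** DCR, CRR and the other secondary rates are covered by explicit text. For the section 5.12.6 subgroups and the forest plot no code is printed, so reuse is likely but not documented.

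**Conclusion.** The code is wrong as written. It reverses the sign of the primary effect estimate and of both its intervals: about -28 points instead of +28 at the design rates, and -27.8 (95% CI -46.6 to -9.0) instead of +27.8 (9.0 to 46.6) for 23/54 versus 4/27. The same reversal applies to DCR and CRR.

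This rests on the SAP's stated sort order and on standard PROC FREQ conventions; no SAS run was made. The reversal does not depend on the illustrative counts, which matters because SAP section 9 says the study ended early and the analysed sample may not be 54 and 27. The error lies in the reported estimate, not in the hypothesis test or the go/no-go decision. It must still be corrected before the analysis is run, because it concerns the direction of the primary result.

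**What to change.** 1. In SAP section 5.12.2, replace `riskdiffcol2` with `riskdiffcol1`. Keep the sort order and `XPR_FISH`.
2. State in the text that the risk difference is combination minus pembrolizumab, and label the table and forest-plot axis accordingly.
3. Add a programmed check that the reported difference equals the two displayed ORRs subtracted in that order.
4. Make the same change wherever the code is reused: DCR, CRR, ORR by CPS, the other subgroup tables and the ORR/DCR forest plot.
5. Check any interim output already produced. SAP section 11 marks the ORR/DCR table and its by-CPS version for the interim.

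The cost is one word of code, one sentence of text and a simple check, with no statistical downside. SAP section 5 requires amendments to be approved before database lock and later changes to go into an addendum, so with the final analysis brought forward the correction should be made now.
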